8.3. Secondary objectives

The secondary objectives of the Registry are to:

1. Estimate the contribution of suspected risk factors to adverse events:
 - the proportion of patients with total and individual thrombotic events who did not receive heparinisation monitoring as recommended in the SmPC (regarding the risks related to heparinisation monitoring)
 - the proportion of patients with anaphylactic reactions who had previously been exposed to aprotinin (solution or fibrin sealant containing aprotinin) in the last 12 months

2. Estimate information concerning:
 - the proportion of pregnant and lactating women
 - the proportion of patients undergoing repeat isolated CABG
 - the proportion of patients having a concomitant use of drugs that affect haemostasis (including antiplatelet therapy) and/or non-VKA oral anticoagulant considered as active at time of surgery and relating safety outcomes when aprotinin is used in those patients
 - the proportion of patients over 75 years of age and outcomes: the proportion of these patients requiring re-operation for bleeding; the mortality rate

3. Estimate optional information according to the national legislation of the countries involved:
 - the proportion of patients exposed to aprotinin for cardiothoracic surgery which indications are outside isolated cardiopulmonary bypass graft surgery
 - the proportion of patients exposed to aprotinin in the paediatric population
 - the proportion of patients exposed to aprotinin for indications other than cardiothoracic surgery

Table 1: Summary of safety concerns from current RMP

Important identified risks	Anaphylaxis Influence of previous exposure to fibrin and aprotinin Renal impairment Embolic and thrombotic events Anticoagulant monitoring
Important potential risks	/
Important identified drug interactions	Aminoglycoside antibiotics related to renal dysfunction
Important identified interactions with other products	Test for Activated Clotting Time related to risk of thrombosis and embolic events.
Missing information	Off-label use Experience in pregnancy and lactation Safety in patients over 75 years of age Use in paediatric population Concomitant use of: 
 - drugs that improve haemostasis - non-VKA oral anticoagulants

9. Research methods

9.1. Study design

The Nordic Aprotinin Patient Registry is a multicentre, non-interventional Post Authorisation Safety Study with active surveillance via patient exposure registry. The main objective is to record the proportion of patients exposed to aprotinin in accordance with the authorised indication.

The Nordic Aprotinin Patient Registry in participating countries in Europe is designed to be easy-to-use and to fit with standard clinical practice.

The Registry is intended to record utilisation information on virtually all patients at cardiac surgery centres exposed to the product beginning from the day that Nordic Aprotinin becomes available to the market, and continuing for at least three years thereafter.

To have access to Nordic Aprotinin and to become a participating centre, cardiac surgery centres have to commit to enrol in the Registry (cf. restricted distribution described in Annex 5). Thus, it is expected that virtually all patients who receive Nordic Aprotinin at all participating cardiac surgery centre in participating countries in Europe will be included in the Registry. Any use in patients outside cardiothoracic surgery is anticipated to be negligible due to the limitation of supply to cardiothoracic centres and the lack of demand in other surgical procedures; however if there is any such use it will be monitored carefully and discussed in the PSUR.

The Registry will collect **prospectively** information on the number of patients who receive Nordic Aprotinin by centre, the recorded indication (cardiac surgical procedure and pre-operative assessment of risk of major blood loss for which Nordic Aprotinin was administered), the characteristics, including risk factors, of the patients who receive Nordic Aprotinin, and the conditions of use, including adherence to instructions for administration in the approved SmPC.

However, if this proposed prospective data collection for all patients exposed to aprotinin is not possible from a national legal point of view, this topic will be discussed with the national concerned authority prior to launch.

The Registry will also collect additional information from healthcare professionals relevant to patient characteristics that may be related to the decision to use Nordic Aprotinin.

9.2. Setting and study population

The Registry is intended to collect data for all patients exposed to Nordic Aprotinin at all cardiac surgical centres fulfilling criteria of the restricted distribution (cf. Annex 5) in participating countries in Europe for at least three years following Nordic Aprotinin's return to the market.

Nordic will have no influence on the selection of any cardiac surgery centres that wish to participate.

The decision to treat with Nordic Aprotinin will be made by the treating physician(s) according to clinical judgment.

During training to healthcare professionals, Nordic will insist on the fact that all patients exposed to aprotinin have to be enrolled in the Registry. Furthermore, the use of the Registry by concerned cardiac surgery centres will be continuously monitored, and Nordic will remind potential non-responders to use the Registry. It is fundamental to the study that patients are entered consecutively and none are excluded from the study.

Inclusion Criteria:

- All patients exposed to Nordic Aprotinin at all participating cardiac surgical centre fulfilling criteria of the restricted distribution in participating countries in Europe.

Exclusion Criteria:

- None

Patients may refuse to have their personal data entered in a database (even if those are anonymised), so those concerned patients will be entered in the Registry with an anonymous sequential number (relating data will not be entered) with the indication "refused to participate to the Registry". This will allow assessing the number of refusals.

The decision to terminate the Registry will be taken in agreement with the PRAC. A centre's commitment to enrol in the Registry will be a prerequisite to that centre's access to Nordic Aprotinin.

9.3. Variables

The design of the Registry follows the template of the reports of the European Association for Cardio-Thoracic Surgery (EACTS) with additional data assessment relevant to the specific needs for recording the use and safety monitoring, including haemostatic monitoring, of the use of aprotinin.

It is recognised that the success of the Registry requires adequate entry of the data. Data entry in previous European Association of Cardio-Thoracic Surgery (EACTS) registries has been very variable by region and by hospital (cf. Fourth EACTS Adult Cardiac Surgical Database Report 2010). This is primarily linked to the time needed to capture data that should take no more than 10-15 minutes according to experts in this field. The collection of data is therefore divided into Key Pages and non-key pages. The **Key Pages** include the Key Data: patient demography and all of the major outcomes of identified or potential hazards in the use of aprotinin, that includes adverse drug reactions such as allergic reactions, renal dysfunction and its relationship to aminoglycoside antibiotics, coagulation control and the use of heparin and the major outcomes of renal failure, myocardial infarction, stroke and other thrombotic effects. Those Key Data allow answering the research question and objectives of this study. These are marked with an asterisk below and by different colours in the web-based Registry.

The Key Data will be the minimum information required for each patient included in the Registry.

Considering the previous experiences with entry of data into registries it is likely that not all users would return complete or nearly complete data entry even for the Key Pages. In order to maximise the level of data entry to the Key Pages Nordic will continually monitor the data entry of each centre. When the Key Data, defined above, are not correctly completed, the site will be encouraged to improve compliance. Similarly post-discharge follow-up data may be difficult to obtain and the availability of data will vary in different Member States and at different centres. However the principal outcomes after follow-up are important and in order to maximise the return Nordic will make arrangements to obtain follow-up data according to the local arrangements and availability of data at each centre.

Other clinical information, further to the Key Data, may be of interest to evaluate some criteria in details. However, collecting these detailed information are time-consuming and cannot be done for all patients. Therefore, Nordic plans to involve academics and medical societies to collect these “non-key data”.

9.3.1. Initial Registry data *

Age;
Gender;
Centre;
Anaesthetist;
Country;
Date of surgery;
Date of admission;
Procedure group;
Use of cardiopulmonary bypass;
Renal impairment;
Last pre-operative creatinine;
Pregnancy;
Lactation;

9.3.2. Operation *

Type of operation elective, urgent, emergency or salvage;
If urgent the reason for urgency;
The number of previous heart operations;
Type of procedure (including valve surgery).

Other surgical procedures will be detailed if relevant. *Note: If the indication for using aprotinin is entirely within the authorised indication up to and at the time of aprotinin administration but complications or unforeseen circumstances arise during surgery and the concerned patient requires further surgery the patient will be considered as an “unintended off-label” case.*

9.3.3. Antiplatelet and anticoagulant therapy considered to be active at operation *

Aspirin, clopidogrel, prasugrel, ticagrelor, dipyridamole, 2b/3a inhibitors, warfarin or phenprocoumon, heparins, direct thrombin inhibitors, direct Factor Xa inhibitors and fibrinolytics. Any other medicine interfering with the primary or secondary haemostasis.

9.3.4. Aprotinin use *

The reason for using aprotinin;
Prior exposure to aprotinin or to fibrin sealants (some contain aprotinin), if available;
Aprotinin IgG test and result if available;
Administration of the test dose to aprotinin and the reaction to the test dose (including anaphylactic reaction);
The loading dose of aprotinin, the pump priming dose and the continuous infusion dose;

The use of another haemostatic.

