8.2. Primary objectives

The primary objectives of the Registry are to:

1. Monitor the pattern of use and record utilisation information:
 - the proportion of patients exposed to aprotinin in accordance with the authorized indication
2. Measure the incidence of the following adverse events:
 - death and the distribution of the primary cause of death
 - thromboembolic events; the total and individual incidence of myocardial infarction, stroke and other thromboembolic events recorded
 - incidence of renal dysfunction defined as a rise in creatinine from pre-operative to post-operative levels of > 0.5 mg/L, and the incidence of renal dialysis
 - the numbers having an anaphylactic response to aprotinin
3. Measure the effectiveness of risk minimisation measures as described in the RMP and close monitoring of adherence to the SmPC recommendations:
 - the proportion of patients receiving heparinisation monitoring as recommended in the SmPC
 - Proportion of patients with a minimal ACT-celite below 750 seconds
 - Proportion of patients with a minimal ACT-kaolin below 480 seconds
 - the proportion of patients with a post-operative renal dysfunction defined as a rise in creatinine from pre-operative to post-operative levels of > 0.5 mg/L or requiring dialysis known to have received aminoglycoside antibiotics
 - the proportion of patients exposed to aprotinin without the use of test dose (or antibody test)
 - the proportion of patients administered with the recommended posology
 - the proportion of patients administered with less than 2.5 million KIU
 - the proportion of patients administered with more than 7 million KIU

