9.3.7. Post-operative*

Reoperation if required with reason for re-operation;

The occurrence of post-operative stroke, post-operative myocardial infarction, other post-operative embolic or thrombotic event, and new post-operative dialysis and relative date;

Post-operative serum creatinine level;

Time to recover renal function baseline value, if available;

Any post-operative use of an aminoglycoside antibiotic;

The occurrence of multisystem failure;

Post-operative blood loss;

Status at discharge and if dead the primary cause of death before discharge;

Date of discharge (and post-operative stay).

Note: the average time-to-events for the abovementioned post-operative events are considered the following: less than one day for reoperation for bleeding (Karthik 2004), one day for renal failure (Rosner 2006), 3 days for stroke (Schwann 2007, Hogue 1999, Dafer 2006), 3 days for myocardial infarction (Thygesen 2007), and 6 days for deep vein thrombosis (Hogue 2006). All abovementioned post-operative events have to be collected at any time, even if those occur after the average time-to-events as published in the literature.

The non-key pages are the following:

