9.5. Study size

All patients exposed to Nordic Aprotinin, at all participating cardiac surgical centres in European countries with marketing authorisation, are intended to be included during the study.

The study is designed primarily to monitor the pattern of use and record utilisation information such as the proportion of patients exposed to aprotinin in accordance with the authorized indication.

Considering that the registry of Great Britain & Ireland recorded just over 400,000 operations in 5 years and that the US one collected around 280,000 operations/year^{15,16}, we could postulate that, across Europe, at least 300,000 patients are undergoing cardiac surgery.

Thus, we estimate the sample size based on the occurrence of events of specific interest (such as type of procedure, death, thromboembolic, stroke ...) with a reasonable precision.

To obtain 95% confidence interval with a maximum margin error of 1.56%, 3,951 patients should be included. This margin error is the maximum one that can be obtained: it is the one based on the assumption that an event of interest is observed in 50% of patients (meaning a 95% CI of [48.44% ; 51.56%]). In all other cases (i.e. event of interest observed in less or more than 50%), precision will only be better (less than 1.56%).

There is no a priori calculation of power for this study because the main primary objective is descriptive rather than inferential and because the adverse event included in the other primary objectives such as in-hospital mortality, thromboembolic events or renal dysfunction are dependant of aprotinin's pattern of use.

Taking into account an exclusion rate of 25% (patient refusing data collection, un-exposed to aprotinin in the course of cardiac surgery with CPB, or undergoing off pump surgery), the number of patients to include is 5,268.

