11.2.1. Reporting of Adverse Events

All other safety information (not suspected to be associated to Nordic Aprotinin) will be included by the Investigator in the eCRF.

This information will be recorded in the Registry and reviewed on a continuing basis allowing recognition of any pattern that may be of cause for concern of a particular hazard in the overall use of Nordic Aprotinin or at the level of an individual country or centre.

All safety information will be included in the interim and final study reports of the Registry which will be submitted to the PRAC (and other Competent Authority if required) via PSUR.

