11.2.2. Reporting of Adverse Drug Reactions

Any adverse drug reaction for which a causal relationship with Aprotinin is reasonably possible must be reported immediately (or at least within 24 hours) by the Investigator to the national or regional Pharmacovigilance centre of a Competent Authority or directly to the Nordic Pharmacovigilance department.

Via routine pharmacovigilance reporting ways:

The Investigator can use the Routine pharmacovigilance reporting ways (such as phone, email and fax).

The Investigator could complete the Adverse Event Report Form (please refer to Annex 3) to report all adverse events suspected to be associated to Nordic Aprotinin and send it to the Nordic Pharmacovigilance department by email and/or fax.

Nordic Group Pharmacovigilance department:

[contact]

[contact]

Email: [contact]

Or

Via the Registry:

In addition to the routine Pharmacovigilance activities, Nordic plans to use the Registry to help physicians report adverse drug reaction.

To do this, Nordic added a “link with Nordic Pharmacovigilance department” in the Registry. Indeed, the Registry is a web-based registry, so it allows a direct link between the end-users (healthcare professionals) and Nordic. In case the patient experiences an adverse event and the physician considers it is associated with Nordic Aprotinin, the physician can directly report the adverse drug reaction via the Registry. This can be done at 3 pages of the Registry: “Aprotinin use”, “Post-operative”

and “Post-discharge follow-up”. The physician can describe the adverse drug reaction, inform its seriousness, the start and end dates and the outcomes.

Then, a form is generated and immediately transferred to the Pharmacovigilance and medical departments of Nordic Group, as well as local safety officer of the concerned country by email.

This information regarding these adverse drug reactions is processed, entered into the Nordic Safety Database, assessed and reported to the Competent Authorities, if applicable, according to the regulation in force. Those adverse drug reactions will be discussed in PSUR according to the regulation in force. A close monitoring will be performed for risks mentioned in the RMP.

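### Anaphylaxis is a primary outcome, but the listed Key Data itemise a reaction only to the test dose; other cases depend on adverse drug reaction reports that no step matches back to registry patients

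*Protocol*

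**What the plan says.** Protocol Section 8.2, primary objective 2, includes "the numbers having an anaphylactic response to aprotinin", with no restriction to one part of the dosing. Section 8.3 uses the same cases as the denominator for prior exposure in the last 12 months. Section 9.7 lists anaphylaxis among the outcomes for each report.

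Section 9.3 states that the Key Data include allergic reactions and are sufficient to answer the objectives. In the itemised list that follows:

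- Section 9.3.4 has "Administration of the test dose to aprotinin and the reaction to the test dose (including anaphylactic reaction").
- The main-dose item in the same section reads "The loading dose of aprotinin, the pump priming dose and the continuous infusion dose". It records doses, not reactions.
- The post-operative event item in Section 9.3.7 reads "The occurrence of post-operative stroke, post-operative myocardial infarction, other post-operative embolic or thrombotic event, and new post-operative dialysis and relative date". Nothing else on that page concerns an allergic or anaphylactic reaction, and the post-discharge list in Section 9.3.8 has no such item.

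Patients without a test dose are expected: Section 8.2 makes "the proportion of patients exposed to aprotinin without the use of test dose (or antibody test") a primary measure.

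Section 11.2.2 requires suspected ADRs to be reported within 24 hours, "by the Investigator to the national or regional Pharmacovigilance centre of a Competent Authority or directly to the Nordic Pharmacovigilance department". It offers phone, email and fax, or a link on three Registry pages (Aprotinin use, Post-operative, Post-discharge follow-up) that generates a form sent to the sponsor. For the eCRF, Section 11.2.1 says: "All other safety information (not suspected to be associated to Nordic Aprotinin) will be included by the Investigator in the eCRF".

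**The concern.** The objective is wider than the variable list that is meant to serve it. A reaction to the loading, pump-prime or infusion dose has no listed item, and the test-dose reaction item cannot apply to a patient who had no test dose. Such cases enter the count only if a physician suspects causality, files a separate report, and that report is later linked to the registry patient. The last step is not described.

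This has two consequences. The registry count of a primary outcome can be biased downward. And because no listed item requires an answer for every patient, an empty record may mean no reaction, a reaction reported elsewhere, or a reaction not reported. The secondary measure of prior exposure among anaphylaxis cases rests on the same incomplete set.

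**Working it through.** **1. Objective against variable list**

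| Situation | Covered by primary objective 2 | Listed item in Section 9.3 | Other route |
|---|---|---|---|
| Reaction to the test dose | Yes | Yes (9.3.4) | ADR report |
| Reaction to loading, pump-prime or infusion dose | Yes | None | ADR report only |
| Any reaction in a patient given no test dose | Yes | None that can apply | ADR report only |

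The general statement in Section 9.3 that allergic reactions are Key Data is therefore met by the list only in the first row.

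**2. Routes for an ADR report and what returns to the registry**

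- Registry link: optional and generic; the form goes to the sponsor's pharmacovigilance and medical departments and the local safety officer.
- Phone, email or fax: goes to the sponsor's pharmacovigilance department.
- National or regional authority centre: satisfies the duty in Section 11.2.2 without a report to the sponsor.

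For none of these does the protocol describe matching the case to a registry patient. The cross-check in Section 9.9 compares sales with patients and doses entered, and Section 9.8.2 provides central review of eCRF data. Neither would reveal an event that has no item.

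**3. The protocol's own figures**

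Inputs: n = 3,951 (Section 9.5); frequency of allergic and anaphylactic reactions between 1/10,000 and 1/1,000 (Section 9.7).

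- Half-width at p = 0.5: 1.96 × √(0.25/3,951) = 1.559%, which reproduces the stated 1.56%.
- The rare-event table in Section 9.9 follows from ln(0.05)/ln(1 − f), the size giving a 95% chance of at least one case. For f = 1/1,000 this is 2,994; for f = 1/10,000 it is 29,956. Both agree with the table, and both assume that every case is captured.

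**4. Expected cases**

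- 3,951 × 1/10,000 = 0.4 and 3,951 × 1/1,000 = 4.0.
- Chance of at least one case, 1 − (1 − f)^3,951: 33% and 98%.

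**5. Sensitivity to lost cases (illustrative; no capture rate is given)**

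Exact 95% limits with x cases in n patients: lower = Beta quantile 0.025 with parameters (x, n − x + 1); upper = Beta quantile 0.975 with parameters (x + 1, n − x).

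| Cases counted | Rate | Exact 95% CI |
|---|---|---|
| 4 | 0.101% | 0.028% to 0.259% |
| 2 | 0.051% | 0.006% to 0.183% |
| 0 | 0% | 0% to 0.093% |

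If four patients truly reacted and none was counted, the upper limit of 0.093% would appear to exclude 1/1,000 (0.1%). With an assumed capture of 50%, the chance of counting at least one case is 1 − (1 − 0.5f)^3,951: 18% at 1/10,000 and 86% at 1/1,000. At 1/1,000, an assumed capture range of 25% to 100% gives 63% to 98%.

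**The case against.** The strongest reply is that the protocol does provide for these cases. An ADR can be filed from inside the Registry on the Aprotinin use page itself, with description, seriousness, dates and outcome. Reporting is required within 24 hours, and anaphylaxis is an identified risk under close monitoring. Section 11.2.1 promises that all safety information will enter the interim and final reports, and Section 9.7 says details of any anaphylaxis will be given separately. Section 9.9 already concedes limits for events of this frequency and names EudraVigilance as another channel. The eCRF is not shown and may hold a broader item.

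Much of this stands. It would be wrong to infer that a main-dose reaction has no way into the Registry, or that the eCRF certainly lacks a field. What remains is that the link is optional and generic, not answered for every patient; that a report solely to an authority centre is sufficient; and that the promise to include all safety information comes with no matching step. The limitation in Section 9.9 concerns sample size, not capture.

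Two further readings are tempting but unsupported:

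- A reader might infer that a patient who reacts to the test dose and receives no more aprotinin loses analysable status, because Section 9.5 mentions patients "un-exposed to aprotinin in the course of cardiac surgery with CPB". Those words explain a 25% sample-size allowance and do not define an analysis set. Section 9.2 includes all exposed patients and has no exclusion criteria.
- A reader might infer that a comparison with and without a test dose would be distorted in favour of omitting it. No such comparison is planned: test-dose use is not a breakdown variable in Section 9.7, and no objective calls for it.

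**Conclusion.** The point holds as a gap between the objective and the listed data capture. Followed as written, the plan can undercount anaphylaxis, and the registry record alone cannot separate no report from no reaction. The direction of any bias in the count is downward; its size is unknown. With 0.4 to 4 expected cases, the loss of one or two would visibly change the estimate and interval.

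This rests on Section 9.3 being a faithful account of the eCRF, and on no reconciliation procedure existing in documents not shown. The frequency range is the protocol's own and applies when appropriate preventive measures are taken, so it may not describe patients given no test dose. Confidence is moderate for these reasons. The change should be made, since it is inexpensive and concerns a primary outcome.

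**What to change.** Before each report to the Independent Data Safety Monitoring Committee and before the final report, reconcile the sponsor's safety database, including cases received from authorities, with registry records by centre and date of surgery. Count an anaphylaxis case found in either source, and state how many came from each. This remains feasible although Section 5 reports that 3,951 analysable patients were already in the January 2020 extraction.

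For any patients still to be entered, add one Key Data item, answered for everyone whether or not a test dose was given: anaphylactic or allergic reaction to aprotinin (none, or at which dose). This brings Section 9.3.4 into line with the general statement in Section 9.3. If the eCRF already has such an item, Section 9.3 need only say so.

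The cost is some reconciliation work at each data cut and, if data entry is still open, one coded item on an existing page.
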